The goal of this proof-of-concept study is to investigate the effect of ketamine on the symptoms of OCD in adolescents and young adults ages 14-22. The symptoms of OCD are evaluated using a number of validated scales designed to measure their clinical status. The specific aims of the study are as follows:

Aim 1. To assess the acceptability, feasibility and tolerability of a single ketamine infusion in adolescents and young adults with OCD.

Aim 2. To assess the effects of ketamine on OCD severity.

Primary Hypothesis:

Adolescent and young adult OCD patients will have a reduction in OCD symptoms immediately following the ketamine infusion.

Description of Subject Population

Sample #1

Specify subject population Individuals with obsessive-compulsive disorder Number of completers required to accomplish study aims 10 Projected number of subjects who will be enrolled to obtain required number of completers 20

Age range of subject population 14-22 inclusive

Gender, Racial and Ethnic Breakdown

Based on our experience and the demographics of the catchment area served by our institution, we expect the subject racial distribution to be approximately 73% White, 18% Black, 9% Asian, and for the ethnic distribution to be approximately 22% Hispanic. We expect the sample to be 50% female. Description of subject population

We will recruit 10 adolescents and young adults (post-pubertal, ages 14-22) with OCD using similar criteria as in the prior study in adults ¹⁴ with the modification that participants have had at least one adequate trial of an SRI medication and a course of CBT for OCD. They will be free of medication or on a stable dose of an SRI medication, score \geq 16 on the Children's Yale-Brown Obsessive Compulsive Scale (CYBOCS) prior to entering the study and report at least moderate severity of obsessions and/or compulsions.

Recruitment Procedures

Describe settings where recruitment will occur The study will recruit participants from the Anxiety Disorders Clinic (ADC), directed by [name], as

well as the CAPES Evaluation Service and the Children's Day Unit (CDU), which are directed by [name]. The ADC screens over 200 adults (\geq 18) with OCD a year. The CAPES/CDU provides free expert consultation, evaluation, and treatment referrals for children and adolescents suffering from mood and anxiety disorders. OCD self-help organizations such as the International OCD Foundation will be contacted to further publicize the existence of this study.

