- *Feasibility and Safety Assessment*: Columbia-Suicide Severity Rating Scale (C-SSRS)
- Clinical Global Impressions Scale (CGI), Medical History, Treatment History, Family History, OCD Onset form.
- *Medical Assessment:* Physical examination, EKG, Tanner Scale, Safety Labs, Vital Signs and Pregnancy Test (serum)
- If clinically indicated, study clinicians may administer the Social Communication Questionnaire (SCQ) and/or an OCPD assessment based on DSM criteria (uploaded).

Note: If the subject has been screened under IRB protocol #6019R "Evaluation at the NYSPI Child Psychiatry Research Clinic" or IRB protocol #6574 "Novel Medication Strategies Targeting Brain Mechanisms in Pediatric OCD" within 1 month of screening for this study, and do not have any new

medical or psychiatric diagnoses that would prevent study entry, they do not need a repeat ADIS or intake in order to reduce patient burden and promote data sharing.

Co-Morbid Depression: Patients with co-morbid depression will be allowed in the study as long as OCD is primary, the Children's Depression Rating Scale-Revised (CDRS-R) is <60, and patient is not currently suicidal. We would like to include patients with co-morbid MDD since ketamine has been shown to have rapid anti-depressant effects ^{15, 16}; thus, assessing the response of these patients to ketamine would allow us to understand the impact of co-morbid MDD on OCD symptoms (in addition to our main goal of understanding ketamine's effects on OCD patients without co-morbidities).

Washout:

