5 OUTCOMES

- 6.1. Primary Outcomes
- i. Total number of screened participants
- ii. Total number completing
- 6.2. Secondary Outcomes
- i. CY-BOCS score at baseline, 1 week post-infusion, and 2 weeks post infusion
- ii. Children's Depression Rating Scale Revised at baseline, 1 week post-infusion, and 2 weeks post
- 6.3 Adverse Outcomes
- i. Adverse events will be assessed throughout the study period
- ii. Suicidality will be obtained with the Columbia-Suicide Severity Rating Scale (C-SSRS).

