3 PROCEDURES

We will recruit 5 adolescents and young adults (post-pubertal, ages 14-20) with OCD using similar criteria as in our prior ketamine study (Rodriguez et al. 2013) with the modification that participants have attempted at least one trial of a standard treatment (i.e., SRI and/or CBT). They will be free of medication and have at least moderate OCD severity (rating on Children's Yale-Brown Obsessive-Compulsive Scale [CY-BOCS] of at least 16) and near constant obsessions. After baseline assessment and evaluation, patients will receive a single infusion of intravenous ketamine 0.5 mg/kg. Obsessional severity will be evaluated at baseline, during the ketamine infusion and during post-infusion observation using the OCD-Visual Analogue Scale; OCD severity will be evaluated using the Children's Yale-Brown Obsessive Compulsive Scale (CY-

BOCS) and Yale-Brown Obsessive Compulsive Challenge Scale (Y-BOCCS) at weekly intervals for 2 weeks and 3-months following after the infusion; illness severity will be rated using the Clinical Global Impressions Severity Scale (CGI-S) at weekly intervals for 2 weeks and 3-months following after the infusion.

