6 OUTCOMES

6.1. Primary Outcomes

Primary outcomes will be the changes in the CY-BOCS total score and CGI-S rating from baseline to 14 days post infusion.

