6.2. Secondary Outcomes

Secondary outcomes will be the changes in the OCD-VAS and Y-BOCCS total score from baseline to 14 days post infusion.

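### The revised SAP drops the depression scale without a reason after the data were considered, so no planned output shows mood change beside the OCD ratings or addresses the protocol's MDD question

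*Protocol*

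**What the plan says.** Protocol, Study Procedures, Co-Morbid Depression: "Patients with co-morbid depression will be allowed in the study as long as OCD is primary", CDRS-R is below 60 and the patient is not currently suicidal. The reason given is ketamine's rapid antidepressant effect, and the paragraph adds that "assessing the response of these patients to ketamine would allow us to understand the impact of co-morbid MDD on OCD symptoms". A bracketed remark closing that sentence names a different chief purpose: "in addition to our main goal of understanding ketamine's effects on OCD patients without co-morbidities". The Specific Aims section sets no such limit. There the goal is to "investigate the effect of ketamine on the symptoms of OCD in adolescents and young adults ages 14-22", and Aim 2 is ketamine's effect on OCD severity.

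The protocol counts CDRS-R among its efficacy assessments. It schedules the scale at screening, baseline, 120 minutes after infusion, day 7 and day 14 (Assessment Instruments).

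The SAP document holds two versions. In the initial one, section 3 covers depressive as well as OCD severity, and Secondary Outcomes lists "Children's Depression Rating Scale Revised at baseline, 1 week post-infusion, and 2 weeks post". In the revised one, section 3 no longer names CDRS-R. It does name CGI-S: "illness severity will be rated using the Clinical Global Impressions Severity Scale (CGI-S". The outcomes are now:

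- "Primary outcomes will be the changes in the CY-BOCS total score and CGI-S rating from baseline to 14 days post infusion"
- "Secondary outcomes will be the changes in the OCD-VAS and Y-BOCCS total score from baseline to 14 days post infusion"

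The revised section 8.2 says that the plan was changed after study completion and after considering the data. The change that it describes is from mixed-effects regression to paired t-tests.

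**The concern.** The protocol chose to enrol patients with depression and treat them with a drug that it describes as rapidly antidepressant, in a study with no control arm. A reader of the results will ask whether mood moved when the OCD ratings moved. The initial SAP would have shown this through CDRS-R. The revised SAP would not.

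The loss matters most for CGI-S, which is now a primary outcome. The SAP describes it as a rating of illness severity, and the protocol describes the CGI as a rating of the patient's condition. Neither says that the rating is confined to OCD.

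There is also a reporting issue. A listed outcome disappears in a revision made after the data had been considered, and the stated explanation does not cover its removal. The results are meant to support a grant application for a randomised trial, so the record of what was planned, collected and dropped should be complete.

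**Working it through.** The documents give no power, SD or effect size for this point, so there is no planned figure to reproduce. The check is mainly a comparison of texts.

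**1. Depression in the three texts**

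| Item | Protocol | Initial SAP | Revised SAP |
|---|---|---|---|
| CDRS-R in procedures | Screening, baseline, 120 min, day 7, day 14 | Yes, weekly for 2 weeks (section 3) | Not named (section 3) |
| CDRS-R as outcome | An efficacy assessment | Secondary (6.2) | None (6.1, 6.2) |
| CGI-S as outcome | Rated, not designated | No | Primary (6.1) |
| MDD status in the analysis | Response of these patients to be assessed | No; covariates are sex and age (8.2) | No; no covariates (8.2) |
| Groups analysed | Not specified | One (section 4) | One (section 5) |
| Reason for dropping CDRS-R | – | – | None; 8.2 explains the change of test only |

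Three things follow. The revision removed the only planned depression outcome. It did not introduce pooling. Neither SAP version used MDD status, so the protocol's MDD question had no dedicated analysis at any stage. After the revision it also lost the mood scale. The C-SSRS remains as an adverse outcome, but it rates suicidality, not severity of depression.

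**2. What can be said about size**

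Let p be the share with MDD, m1 their mean CY-BOCS change, and m0 the mean change in the others. The pooled mean is (1 − p) × m0 + p × m1 = m0 + p × (m1 − m0). It therefore differs from the non-MDD mean by p × d, with d = m1 − m0.

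The documents give neither p nor d, nor the sign of d. Purely as an assumption, take 5 participants and a d of 5 points in either direction:

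- 0 of 5 with MDD: 0
- 1 of 5: 0.2 × 5 = 1.0 point either way
- 2 of 5: 0.4 × 5 = 2.0 points either way
- 3 of 5: 0.6 × 5 = 3.0 points either way

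The range runs from −3.0 to +3.0 and includes zero. It shows only that size and direction cannot be fixed from the documents.

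**3. What restored data could support**

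Sample sizes are 5 (revised SAP, section 3) and 10 (protocol). A two-sided 5% level is assumed from the planned 95% intervals.

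- The half-width of a 95% interval for a mean change is t(0.975, n − 1) / √n in SD units. This gives 1.24 SD at n = 5 and 2.48 SD in a subgroup of 3.
- The smallest correlation between CY-BOCS change and CDRS-R change that reaches p < 0.05 is t / √(t² + n − 2), with t = t(0.975, n − 2). This gives 0.88 at n = 5 and 0.63 at n = 10.

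Only very strong relations could be detected. The added output should be descriptive and should not include a subgroup test.

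**The case against.** The strongest defence is that the pooled analysis answers the governing objective. The Specific Aims set no co-morbidity limit, and both SAP versions repeat Aim 2. The main-goal wording is one parenthesis in an eligibility paragraph. That stands: a reader might infer that the pooled mean estimates the wrong population, but the documents support only an inconsistency in the protocol that should be reconciled.

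The defence can add that mood has a limited route into the results. CY-BOCS, OCD-VAS and Y-BOCCS, three of the four efficacy outcomes, are OCD scales that mood could reach only indirectly. OCD must be the principal disorder, and patients with CDRS-R of 60 or more are excluded. The case for CGI-S rests on how its description is worded. This also stands. A reader might infer that an improvement under the revised plan would really be an antidepressant effect. The documents do not support that: they give no MDD count, patients with depression could improve less than the others, and OCD relief could itself lift mood.

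None of this explains why a scheduled and previously listed outcome was removed, and none of it puts mood data beside the OCD ratings.

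**Conclusion.** The point holds as an omission. CDRS-R was scheduled in the protocol and was a secondary outcome in the initial SAP. It is absent from a revision made after the data were considered, and no reason is given. As a result, no planned output shows mood change beside the OCD ratings or addresses the MDD question, while CGI-S has become a primary outcome.

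The effect on the pooled mean is unknown in size and direction, and it is zero if no participant had MDD. The illustrative range above rests wholly on assumed inputs. A reader might also infer that CDRS-R was dropped because of what it showed. The documents give the timing but no motive, so the timing should be disclosed and no intent presumed. Correction is worthwhile because it is cheap, but it will not make an uncontrolled pilot of 5 to 10 participants able to attribute change to OCD or to mood.

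**What to change.** - Restore CDRS-R change from baseline at days 7 and 14 as a secondary outcome in the revised SAP.
- Add a descriptive per-participant listing: MDD status from the ADIS, baseline CDRS-R, and change in CY-BOCS, CGI-S and CDRS-R. Where a participant's ADIS was carried over from another screening protocol, take MDD status from there.
- Disclose that CDRS-R was dropped after study completion and consideration of the data, and give the reason.
- Reconcile the main-goal wording in the co-morbid depression paragraph with the Specific Aims.
- State that this uncontrolled study cannot separate an OCD-specific effect from a mood effect.

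The non-MDD subgroup should not be promoted to a main result. It would be chosen after the data were considered and would be too small for inference.

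The cost is some SAP wording and one more table or listing, from assessments that the protocol already schedules. The output is descriptive only.

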At the conclusion of each test day (after the 2-hour observation period), the study MD will evaluate the patient to determine if the effects of the study drug infusion have resolved to the point that subjects are safe to return home. These evaluation criteria will consist of absence of significant deviations from baseline in vital signs, gait, mental status exam, and assessments listed in the study flowchart including BPRS and CADSS scales. In the case of an adverse psychiatric event, patients will be admitted either to the Pediatric Emergency Department at New York Presbyterian Hospital or directly to the fourth floor inpatient unit (4 Center) at the New York State Psychiatric Institute, if clinically appropriate. The PALS-certified pediatrician will be available for the duration of the post-infusion 2-hour observation period. Once patients have been cleared by the MD to go home, adolescents will be required to leave the Irving Center with a parent or guardian and young adults will be required to leave the Irving Center with a parent or guardian or support person identified by the young adult.

Day 2 – 14: Post-Infusion Monitoring & Assessments

After the ketamine infusion, participants will be monitored closely for a 2-week period. The primary measure of change in OCD symptoms will be the Children's Yale-Brown Obsessive Compulsive Scale (CYBOCS). This, along with additional measures will be administered during this 2-week period as follows:

• *Days 2-6 post-infusion:* OCD-VAS and YBOCCS are administered during optional daily phone calls (except when they have an in-person visit on day 3 or 4, during which these will be administered in person).

The in-person visit between day 2-6 post infusion is not a required study visit and will be offered on a caseby-case basis. During this period, if the study MD determines that an in-person visit is needed or if the participant requests an in-person appointment, they will be asked to come to the clinic and will complete the following assessments. Otherwise these assessments will be completed over the phone.

- Day 3 or 4: Participants come to the CDU to complete the following assessments:
 - MD ratings: Columbia-Suicide Severity Rating Scale (C-SSRS), Young Mania Rating Scale (YMRS), Clinician Administered Dissociative States Scale (CADSS), Brief Psychiatric Rating Scale (BPRS), Clinical Global Impressions Scale (CGI).

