 - o Medical assessment: Vital Signs and Pregnancy Test (urine) for female participants

Note: If a patient's score on the Global Improvement section of the CGI is a 6 ("much worse") or 7 ("very much worse") compared to baseline at the day 3 or 4 study visit, the clinician will take the

patient off the protocol and initiate the 3-month open clinical treatment offered to all patients at the end of the study.

- *Day 7 post-infusion:* Participants complete the following assessments at the CDU or over the phone (if participants live far away):
 - IE ratings: Children's Yale-Brown Obsessive Compulsive Scale (CYBOCS), Children's Depression Rating Scale-Revised (CDRS-R), Clinical Global Impressions Scale (CGI).
 - MD ratings: Columbia-Suicide Severity Rating Scale (C-SSRS), Young Mania Rating Scale (YMRS), Clinician Administered Dissociative States Scale (CADSS), Brief Psychiatric Rating Scale (BPRS), Clinical Global Impressions Scale (CGI).
 - Self-report forms: OCD Visual Analogue Scale (OCD-VAS), Yale-Brown Obsessive Compulsive Challenge Scale (YBOCCS), Child Obsessive-Compulsive Impact Scale-Revised (COIS-R).
 - Medical assessment: Vital Signs and Pregnancy Test (urine) for female participants

Note: If a patient's score on the Global Improvement section of the CGI is a 6 ("much worse") or 7 ("very much worse") compared to baseline at the day 7 study visit, the clinician will take the patient off the protocol and initiate the 3-month open clinical treatment offered to all patients at the end of the study.

- *Day 8-13 post infusion:* OCD-VAS and YBOCCS are administered daily during optional phone calls.
- *Day 14 post-infusion:* Participants come to the CDU to complete the following assessments:
 - IE ratings: Children's Yale-Brown Obsessive Compulsive Scale (CYBOCS), Children's Depression Rating Scale-Revised (CDRS-R), Clinical Global Impressions Scale (CGI).
 - MD ratings: Columbia-Suicide Severity Rating Scale (C-SSRS), Young Mania Rating Scale (YMRS), Clinician Administered Dissociative States Scale (CADSS), Brief Psychiatric Rating Scale (BPRS), Clinical Global Impressions Scale (CGI).
 - Self-report forms: OCD Visual Analogue Scale (OCD-VAS), Yale-Brown Obsessive Compulsive Challenge Scale (YBOCCS), Child Obsessive-Compulsive Impact Scale-Revised (COIS-R).
 - o Medical assessments: Safety labs, vital signs, pregnancy test (urine) for female participants.

Follow-up Treatment

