8.2. Statistical Tests

In the initial SAP, we proposed a mixed-effects regression to analyze the potential efficacy of the ketamine infusion. After study completion and careful consideration of the data collected, we decided to change the SAP to compare the mean differences of the primary and secondary outcomes between the baseline assessment and 14 days post infusion using paired sample t-tests.

The normal distribution of the differences between the paired values will be tested using the Shapiro-Wilk test and outliers will be reviewed using box plot diagrams. Estimated t-values, 95% confidence intervals, and p-values will be presented for each outcome variable.

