8 MISSING VALUES

Missing values will be excluded from the statistical tests pairwise.

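### The revised SAP tests OCD-VAS and Y-BOCCS at day 14 only, although readings are offered daily for two weeks, so a null result cannot separate no effect from one that faded

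*Protocol*

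**What the plan says.** **Protocol, Day 2 – 14: Post-Infusion Monitoring & Assessments.** For days 2-6, "OCD-VAS and YBOCCS are administered during optional daily phone calls". For days 8-13, "OCD-VAS and YBOCCS are administered daily during optional phone calls". The day-7 and day-14 self-report forms both include "OCD Visual Analogue Scale (OCD-VAS), Yale-Brown Obsessive Compulsive Challenge Scale (YBOCCS), Child Obsessive-Compulsive Impact Scale-Revised (COIS-R"). Under Assessment Instruments, OCD-VAS is a one-item scale for a rapid time frame and YBOCCS a brief self-report scale for rapid change. Both are also rated before, during and after the infusion, following a flowchart that is not part of these documents.

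**Revised SAP (the second of the two SAP texts).** Section 6.2: "Secondary outcomes will be the changes in the OCD-VAS and Y-BOCCS total score from baseline to 14 days post infusion". Section 8.2 compares means "between the baseline assessment and 14 days post infusion using paired sample t-tests", and "Estimated t-values, 95% confidence intervals, and p-values will be presented for each outcome variable". On missing data: "Missing values will be excluded from the statistical tests pairwise". The primary outcomes in section 6.1 (CY-BOCS and CGI-S) are also changes from baseline to day 14, so no planned test looks at an earlier time.

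**Schedule in revised SAP section 3.** It has the "Yale-Brown Obsessive Compulsive Challenge Scale (Y-BOCCS) at weekly intervals for 2 weeks and 3-months following after the infusion". It places OCD-VAS at baseline, during the infusion and in post-infusion observation only. The daily calls do not appear, nor does the day-14 OCD-VAS reading that section 6.2 relies on.

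**The concern.** The primary hypothesis in the protocol is a reduction immediately after the infusion. The rationale cites an adult trial in which the effect lasted up to one week in half of the patients, and asks whether effects in youth are similar. The section on minimizing risks expects relief to be temporary for some participants. The only planned contrast falls at two weeks, after the period over which the adult effect was reported.

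A day-14 result near zero would therefore fit two quite different conclusions: ketamine did nothing, or it worked and wore off. A decision on a full-scale trial depends on which is true. The calls are the only source of near-daily information on this, and no planned analysis uses them. The day-7 and infusion-day readings of the two scales are unused as well.

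The pairwise rule adds a smaller cost. A participant without a day-14 score leaves the test, whatever the earlier readings show.

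**Working it through.** The documents give no SD, correlation, effect size, power or call completion rate for either scale, so there is no figure to reproduce. All correlations, effect sizes and half-lives below are assumptions.

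**1. Readings available.** Days 2-6 give 5, day 7 gives 1, days 8-13 give 6 and day 14 gives 1: 5 + 1 + 6 + 1 = 13 at most, of which 7 fall in days 8-14. The planned test uses 1 of them.

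**2. Precision of the day-14 contrast.** The 95% CI half-width is t(0.975, n−1)/√n, in SDs of the change score. The documents give different n: 5 recruited (SAP section 3), 10 completers required (protocol, Description of Subject Population), and 4 completed at the time of the protocol review.
- n = 4: 1.59
- n = 5: 2.776/√5 = 1.24
- n = 10: 0.72

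Losing one of five participants through a missing day-14 score moves the half-width from 1.24 to 1.59 SD.

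**3. What day 14 can miss.** Assume an immediate effect of 2 SD that decays with a 7-day half-life, with time counted in days from the infusion.
- At day 14 the remaining effect is 2 × 2^(−14/7) = 0.5 SD.
- The mean over days 2-7 is 2 × (0.820 + 0.743 + 0.673 + 0.610 + 0.552 + 0.500)/6 = 2 × 0.650 = 1.30 SD.
- Two-sided 5% power of the paired t-test at n = 5 is 91% for 2 SD and 14% for 0.5 SD.

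Even a large early effect would then usually give a non-significant day-14 test.

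**4. Do the other days sharpen the day-14 change itself?** With complete data and a separate mean for each day, no: the SE ratio is 1.00. A gain needs an assumed shape. With a straight line over days 8-14 and independent errors, the variance of the fitted day-14 value is 1/7 + 9/28 = 0.464. The SE ratio is then √((1 + 0.464)/2) = 0.856 at best.

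**5. Precision of a week-2 mean.** Let r be the between-person variance of true change divided by the within-person day-to-day variance. Let V_m be the variance of the mean of m readings with AR(1) correlation φ, in units of the within-person variance. Against one day-14 reading, with one baseline reading in both cases, the SE ratio is √[(r + 1 + V_m)/(r + 2)].

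| m | r | φ | SE ratio | cut in SE |
|---|---|---|---|---|
| 7 | 0 | 0 | √(1.143/2) = 0.756 | 24% |
| 7 | 1 | 0.3 | √(2.240/3) = 0.864 | 14% |
| 7 | 1 | 0.8 | √(2.641/3) = 0.938 | 6% |
| 7 | 4 | 0.8 | √(5.641/6) = 0.970 | 3% |
| 3 | 0 | 0 | 0.816 | 18% |
| 3 | 4 | 0.8 | 0.986 | 1% |

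At n = 5 with all seven readings, the half-width goes from 1.24 to between 1.24 × 0.756 = 0.94 and 1.24 × 0.970 = 1.20, in SDs of the day-14 change.

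**6. The week-2 mean is a different target.** Under exponential decay with half-life h, the mean over days 8-14 divided by the day-14 effect is (1/7) Σ 2^(j/h), j = 0 to 6. This is 1.17 for h = 14 days, 1.37 for h = 7 and 2.22 for h = 3.

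**The case against.** The case for leaving the plan alone has four parts.

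- **Duration is not a stated aim.** The hypothesis concerns the immediate effect, and the protocol assigns maintenance of response to the 3-month visit. This is true, but a day-14 contrast does not test an immediate effect either, and the 3-month visit follows open treatment.
- **The calls are optional.** A reader might infer that 13 readings per participant exist and 12 are discarded. The documents support only up to 13 offered. If calls were skipped in relation to symptoms, averages over them could be biased. This stands, and is why call counts must be reported.
- **The day-14 estimate is not needlessly imprecise.** A reader might infer that it is. Step 4 shows that the other days add nothing to that quantity without an assumed time course. The 24% figure is a best case for a different quantity.
- **A further endpoint change carries risk.** Section 8.2 says the method was changed after study completion and consideration of the data. Making the week-2 mean the secondary outcome now would be one more late change, towards a target that is larger than the day-14 effect if benefit fades. This stands: the endpoint should not be redefined.

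A reader might also infer that the mixed model in the initial SAP would have used the daily series. Its list of secondary outcomes names only CY-BOCS and the depression scale, at baseline, one week and two weeks.

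**Conclusion.** The point holds as a gap in the analysis and a mismatch between the documents. Up to 13 post-infusion-day readings per scale are offered or scheduled, one is analysed, and SAP section 3 does not describe the schedule in the protocol. The plan cannot show whether benefit appeared and then faded. That conclusion rests on the documents alone and needs no correlation assumption; the 2-SD example only illustrates its size.

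The claim on precision is limited. It applies to a week-2 mean, runs from about 3% to 24% in SE with all seven readings under the assumed r and φ, and shrinks if calls are skipped. The documents do not support replacing the day-14 outcome. A labelled supplement is a cheap improvement.

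**What to change.** 1. Keep change from baseline to day 14 as the secondary outcome in SAP section 6.2.
2. Add a supplementary analysis to section 8.2, stated to have been planned after study completion:
   - plot each participant's OCD-VAS and Y-BOCCS over all available readings, including infusion day and day 7;
   - report mean change from baseline with 95% CI for week 1 (days 2-7) and week 2 (days 8-14), beside day 14;
   - for participants who improved, describe loss of benefit by a rule less sensitive to noise than a single first crossing of one baseline reading, for example two consecutive readings at or above baseline, and mark any missed calls around that time;
   - report calls completed by participant and by day.
3. Reconcile section 3 with the protocol schedule, including the daily calls and the OCD-VAS readings on days 7 and 14.

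The cost is some SAP wording and a little analysis, with no new data. The supplement remains post hoc, optional phone calls may be missed selectively, and the week-2 mean answers a different question from day 14 if the effect is fading. Showing the results side by side with the call counts makes these limits visible but does not remove them.
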